Appendix 13. HAQ-DI³⁵

**Health Assessment Questionnaire - Disability Index (HAQ-DI)[®] Stanford University
 1983 version:**

In this section we are interested in learning how your illness affects your ability to function in daily life.

Please check the response which best describes your usual abilities OVER THE PAST WEEK:

	Without ANY difficulty	With SOME difficulty	With MUCH difficulty	UNABLE to do
DRESSING & GROOMING				
Are you able to:				
-Dress yourself, including tying shoelaces and doing buttons?				
-Shampoo your hair?				
ARISING				
Are you able to:				
-Stand up from a straight chair?				
-Get in and out of bed?				
EATING				
Are you able to:				
-Cut your meat?				
-Lift a full cup or glass to your mouth?				
-Open a new milk carton?				
WALKING				
Are you able to:				
-Walk outdoors on flat ground?				
-Climb up five steps?				

Please check any AIDS OR DEVICES that you usually use for any of these activities:

 Cane	 Devices used for dressing (button hook, zipper pull, long-handled shoe horn, etc.)
 Walker	
 Crutches	 Built up or special utensils
 Wheelchair	 Special or built up chair
	 Other (Specify: _____)

Please check any categories for which you usually need HELP FROM ANOTHER PERSON:

 Dressing and Grooming	 Eating
 Arising	 Walking

Please check the response which best describes your usual abilities OVER THE PAST WEEK:

	Without ANY difficulty	With SOME difficulty	With MUCH difficulty	UNABLE to do
HYGIENE				
Are you able to:				
-Wash and dry your body?				
-Take a tub bath?				
-Get on and off the toilet?				
REACH				
Are you able to:				
-Reach and get down a 5-pound object (such as a bag of sugar) from just above your head?				
-Bend down to pick up clothing from the floor?				

	Without ANY difficulty	With SOME difficulty	With MUCH difficulty	UNABLE to do
GRIP				
Are you able to:				
-Open car doors?				
-Open jars, which have been previously opened?				
-Turn faucets on and off?				
ACTIVITIES				
Are you able to:				
-Run errands and shop?				
-Get in and out of a car?				
-Do chores such as vacuuming or yard work?				

Please check any AIDS OR DEVICES that you usually use for any of these activities:

 Raised toilet seat	 Bathtub bar
 Bathtub seat	 Long-handled appliances for reach
 Jar opener (for jars previously opened)	 Long-handled appliances in bathroom
	 Other (Specify: _____)

Please check any categories for which you usually need HELP FROM ANOTHER PERSON:

 Hygiene	 Gripping and opening things
 Reach	 Errands and chores

Appendix 14. Assessment of Itch (NRS)³⁶

Severity of Pruritus

Select the number that best describes your itching over the past 24 hours (check one number only).

										
0	1	2	3	4	5	6	7	8	9	10
No itching										Worst possible itching

1. VERSION HISTORY

This SAP for study B7981006 is based on the protocol dated 22AUG2016.

Table 1. Summary of Major Changes in SAP Amendments

SAP Version	Change	Rationale
1	Not Applicable	Not Applicable
2	Derivation/update of the prior distribution for placebo response based on the review of baseline data. Changes made to Appendix 4	Availability and review of study baseline SDAI data. The prior placebo distribution depends on current study baseline data.

[figure not shown]
[figure not shown]
[figure not shown]
2. INTRODUCTION

[figure not shown]
This SAP provides the detailed methodology for summary and statistical analyses of the data collected in study B7981006. This document may modify the plans outlined in the protocol; however, any major modifications of the primary endpoint definition or its analysis will also be reflected in a protocol amendment.

2.1. Study Objectives

Table 2. Study Objectives and Endpoints

Primary Objectives:	Primary Endpoints:

 To evaluate the efficacy of PF-06651600 at 8 weeks in subjects with moderate to severe active rheumatoid arthritis. 	
 Change from baseline in simple disease activity index (SDAI) at Week 8.
Secondary Objectives:	Secondary Endpoints:

 To evaluate the safety of PF-06651600. To assess other signs of clinical efficacy over 8 weeks. 	
 Safety and tolerability of PF-06651600 versus placebo; vital signs, laboratory tests, adverse events (AEs) including infections, and Serious Adverse Events (SAEs). Change from baseline in SDAI at Weeks 1, 2, 4, and 6. SDAI low disease activity scale and remission rates at Weeks 4, 6, and 8. Disease activity score (DAS) low disease activity scale and remission rates at Weeks 4, 6, and 8: DAS28-3 (erythrocyte sedimentation

[figure not shown]
	
rate (ESR)), DAS28-3 (C-reactive protein (CRP)), DAS28 -4 (ESR), and DAS28-4 (CRP).
 
The following will also be calculated at Weeks 1, 2, 4, 6, and 8:
 
 • Change from baseline in DAS28-3 (ESR), DAS28-3 (CRP), DAS28 -4 (ESR), and DAS28-4 (CRP). • Change from baseline in high sensitivity C-reactive protein (hsCRP). • Change from baseline in the Tender/Painful and Swollen Joint Count (28). • Change from baseline in the Physician's Global Assessment (PhGA) of Arthritis.

 • To assess the effect of PF-06651600 on patient reported outcome measurements. 	
 • Change from baseline in the Patient's Assessment of Arthritis Pain (PAAP) Visual Analogue Scale (VAS) and Patient's Global Assessment (PtGA) of Arthritis VAS at Weeks 1, 2, 4, 6, and 8. • Change from baseline in the Health Assessment Questionnaire – Disability Index (HAQ-DI) at Weeks 1, 2, 4, 6, and 8.
	   

*Note: Analysis of exploratory endpoints may be further detailed in SAP or exploratory analysis plan. Samples collected for exploratory endpoints may or may not be analyzed and, if analyzed, may or may not be reported in the CSR.

2.2. Study Design

Figure 1. Study Design Schematic

Note: N indicates the total number of completers.

This is a Phase 2a, 8 week randomized double-blind, parallel group, placebo controlled, multi-center study to assess the efficacy and safety profile of PF-06651600 in seropositive subjects with moderate to severe active rheumatoid arthritis with an inadequate response to methotrexate (up to approximately 50% of subjects may also have had an inadequate response to 1 anti- tumor necrosis factor α (TNF α) biologic disease-modifying antirheumatic drug).

Up to approximately 60 subjects may be randomized globally into the study to ensure at least approximately 50 subjects complete 8 weeks of active dosing (assuming a dropout rate of approximately 15%). Subjects will participate in this study for approximately 16 weeks. This includes an up to 5-week screening period, an 8 week treatment period, and a 4 week follow-up period.

After an up to 5 week screening period, eligible subjects will be randomized to receive 200 mg twice a day (QD) of PF-06651600 or placebo (matching tablets for PF-06651600 QD) every day for 8 weeks in a blinded fashion.

3. ENDPOINTS AND BASELINE VARIABLES: DEFINITIONS AND CONVENTIONS

3.1. Primary Endpoint(s)

The primary endpoint for this study is change from baseline in SDAI at Week 8. The SDAI is a continuous composite measure derived from components of the ACR Core Dataset at baseline (Day 1), Weeks 1, 2, 4, 6, and 8.

3.2. Secondary Endpoint(s)

- Change from baseline in SDAI at Weeks 1, 2, 4, and 6.
- SDAI low disease activity scale and remission rates at Weeks 4, 6, and 8.
- DAS28-3 (ESR), DAS28-3 (CRP), DAS28 -4 (ESR), and DAS28-4 (CRP) low disease activity scale and remission rates at Weeks 4, 6, and 8.

The following will also be calculated at Weeks 1, 2, 4, 6, and 8:

- Change from baseline in DAS28-3 (ESR), DAS28-3 (CRP), DAS28 -4 (ESR), and DAS28-4 (CRP).
- Change from baseline in hsCRP.
- Change from baseline in the Tender/Painful and Swollen Joint Count (28).
- Change from baseline in the PhGA of Arthritis.

3.3. Patient Outcomes Research (PRO) Endpoints

- Change from baseline in the PAAP VAS and PtGA of Arthritis VAS at Weeks 1, 2, 4, 6, and 8.
- Change from baseline in the HAQ-DI at Weeks 1, 2, 4, 6, and 8.

CCI

- ACR20, ACR50, and ACR70 responder rates.
- CCI

3.5. Baseline Variables

Below are baseline variables:

- Screening: Demographics and RA history, smoking history, medical history and non RA medications, history of alcohol and drug abuse, height, and weight.
- Day 1: Vital signs (pulse rate, blood pressure), temperature, and complete physical examination.

3.6. Safety Endpoints

Safety will be assessed by the spontaneous reporting of AEs, physical examinations and clinical laboratory results in all subjects who receive at least one dose of the investigational product. Unscheduled safety assessments may be performed at any time during the study to assess any perceived safety concerns.

3.6.1. Adverse Events

An adverse event is considered treatment emergent relative to a given treatment if:

- the event occurs for the first time during the effective duration of treatment and was not seen prior to the start of treatment (for example, during the baseline or run-in period), or
- the event was seen prior to the start of treatment but increased in severity during treatment.

A 3-tier approach will be used to summarize AEs. Under this approach, AEs are classified into 1 of 3 tiers. Different analyses will be performed for different tiers (see [Section 6.7.1](#)).

Tier-1 events: These are pre-specified events of clinical importance and are maintained in a list in the product's Safety Review Plan.

Tier-2 events: These are events that are not tier-1 but are “common”. A Medical Dictionary for Regulatory Activities (MedDRA) Preferred Term (PT) is defined as a tier-2 event if there are at least 4 in any treatment group.

Tier-3 events: These are events that are neither tier-1 nor tier-2 events.

3.6.2. Laboratory Data

Laboratory data will be listed and summarized by treatment in accordance with the Pfizer reporting standards.

3.6.3. Vital Signs

Absolute values and changes from baseline in systolic and diastolic blood pressure, respiratory rate, pulse rate and temperature will be summarized by treatment and visit, according to Pfizer reporting standards.

3.6.4. Electrocardiogram (ECG)

Categorical summary tables will be summarized by treatment and visit using Pfizer reporting standards. A listing of ECG comments on findings and normal/abnormal results will be provided.

4. ANALYSIS SETS

4.1. Intent-to-Treat Analysis Set

An intent-to-treat (ITT) analysis set will include all subjects who were randomized to the study and received at least one dose of the randomized investigational drug (PF-06651600 or placebo).

4.2. Safety Analysis Set

The safety (SAF) analysis set is defined as those subjects who received at least one dose of the investigational drug.

4.3. Other Analysis Sets

None.

5. GENERAL METHODOLOGY AND CONVENTIONS

Final analyses will occur after database lock after Last Subject Last Visit (LSLV).

5.1. Hypotheses and Decision Rules

The null hypothesis that the distribution of SDAI change from baseline at Week 8 is the same between the active and placebo arms will be tested using Bayesian framework outlined in [Appendix 4](#). Statistical separation from the placebo will be observed if the probability of treatment effect Δ^* being greater than zero is over 90%.

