9.1. Sample Size Determination

The primary endpoint of the study will be the change from baseline in SDAI at 8 weeks. The study will enroll approximately 50 completers allocated as follows:

PF-06651600 (200 mg) (N)	Placebo (N)
30	20

Assuming a 15% dropout rate* the study will enroll approximately 60 subjects.

The study will have over 90% power to detect separation from placebo, assuming a 13 point difference in response between the placebo and 200 mg arm (standard deviation is assumed to be 14 points for both arms*) and controlling Type-I error rate at 5% level. More detailed sample size considerations will be discussed in the SAP.

**Based on information from Phase 3 tofacitinib studies.*

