5.2.2. Analyses for Continuous Data

Mixed Effect Model Repeat Measurement (MMRM) for Longitudinal Continuous Data:

The fixed effects of treatment, visit, and treatment-by-visit interaction will be included, along with patient as a random effect. Unstructured covariance matrix will be assumed.

When modeling the change from baseline values, the variable of visit will start with the first post-baseline visit, and the actual baseline value will be included as a covariate. At each visit, estimates of mean values and the mean differences between the active treated group and the placebo group will be derived from the model. The corresponding p-values, standard errors and 95% confidence intervals will also be derived from the model.

Below is an example of potential statistical analysis system (SAS) code:

```
PROC MIXED DATA=XXX;
  CLASS SUBJID TREATMENT VISIT;
  MODEL CHGBASE=TREATMENT VISIT TREATMENT*VISIT BASE/ALPHA=0.05 DDFM=KR;
  REPEATED VISIT/SUBJECT=SUBJID TYPE=UN;
  LSMEANS TREATMENT*VISIT/ALPHA=0.05 CL DIFF;
RUN;
```

Analysis of Covariance (ANCOVA) for Non-longitudinal Continuous Data:

The non-longitudinal continuous data will be analyzed by ANCOVA with treatment as the factor. When modelling change from baseline values, the actual baseline value will be included as a covariate. Active dose group will be contrasted versus placebo.

Below is an example of potential SAS code:

```
PROC MIXED DATA=XXX;
  CLASS TREATMENT;
  MODEL CHGBASE=TREATMENT BASE/ALPHA=0.05;
  LSMEANS TREATMENT/ALPHA=0.05 CL PDIFF;
RUN;
```

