6.1.1. Primary Analysis

The primary analysis will be based on the Bayesian analysis outlined in Appendix 4.

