Appendix 4. ADDITIONAL METHODOLOGY DETAILS

Details of Bayesian analysis of posterior distributions of the SDAI scores

Notation/Definitions

$i = 1, 2, \dots, n$; where n is the total number of patients

x_i^B = Baseline SDAI score for Patient i

x_i^W = Week W SDAI score for Patient i

$y_i = -(x_i^W - x_i^B)$; negative change from baseline SDAI at Week W for Patient i

$I_i^D = \begin{cases} 1, & \text{if Patient } i \text{ received Treatment D} \\ 0, & \text{otherwise.} \end{cases}$

A = Active treated group

P = Placebo treated group

Primary Model – Bayesian Analysis of Covariance

$$y_i = \mu_p^* I_i^P + (\mu_p^* + \Delta^*) I_i^A + \beta(x_i^B - \mu^B) + \varepsilon_i,$$

where $\varepsilon_i \sim N(0, \sigma_\varepsilon^2)$

Prior Models:

$\mu_p^* \sim N(13.7, \sigma^2 = 25)$

$\Delta^* \sim N(0, 10^3)$

$\beta \sim N(0, 10^3)$

$\sigma_\varepsilon^2 = \text{Noninformative inverse gamma } IG(0.001, 0.001)$

Note: μ_p^H is calculated based on commensurability between the historic and current study baseline patient profiles including both arms. The baseline profiles were based on baseline SDAI score prior ant-TNF exposure status. Geographic data was not used in the assessment of the prior distribution.

At least two alternative sensitivity prior models will be considered for μ_p^H , with one being a noninformative prior $N(0, 10^3)$. Also sensitivity models will be considered with ε_i modeled using t distribution with three degrees of freedom.

Data visualization techniques

Table shells of figures displaying the primary endpoint results (see below) will be provided in programming document.

- Distribution of treatment effect Δ^* .
- Display of change from baseline by treatment group based on Bayesian Analysis of Covariance.
- Display of change from baseline by treatment group based on Bayesian Analysis of Covariance vs baseline SDAI.

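### The 90% posterior-probability rule does not carry the protocol's 5% Type I error: one-sided error is about 8% with the placebo prior on target and 10% without borrowing, and the sidedness of the 5% is not stated

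*SAP*

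**What the plan says.** Protocol 9.1 sizes the trial at 30 active and 20 placebo completers. It assumes a 13-point SDAI difference and an SD of 14 in each arm, and claims over 90% power for separation from placebo, "controlling Type-I error rate at 5% level". It does not say one- or two-sided. It adds: "More detailed sample size considerations will be discussed in the SAP".

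SAP 5.1 frames the comparison as a test of a null hypothesis and gives the decision rule: "Statistical separation from the placebo will be observed if the probability of treatment effect" Δ* "being greater than zero is over 90" per cent. SAP 6.1.1 fixes the analysis this applies to: "The primary analysis will be based on the Bayesian analysis outlined in Appendix 4". That appendix gives the placebo mean improvement a N(13.7, variance 25) prior, with vague priors on the effect, the slope and the residual variance. SAP section 1 explains where the placebo prior comes from: "The prior placebo distribution depends on current study baseline data". For sensitivity, Appendix 4 says "At least two alternative sensitivity prior models will be considered for" the placebo mean, one of them noninformative. ANCOVA and MMRM are sensitivity analyses in SAP 6.1.2.

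The SAP text supplied contains no sample size section and no Type I error or power for the 90% rule.

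**The concern.** Both documents speak of separation from placebo. The protocol attaches 5% to that event, and the SAP decides it by a rule with no stated error rate. A posterior probability above 0.90 under vague priors corresponds roughly to a one-sided 10% test, so on its face the rule is looser than 5% on either reading.

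Borrowing adds a second problem. The prior has fixed weight. It does not lose influence when the observed placebo mean disagrees with it, so the false-positive rate depends on how far the true placebo improvement lies from 13.7. Matching the prior to the trial's own baseline SDAI and anti-TNF status makes a large gap less likely, but does not change that mechanism. At stake is what a reader may conclude from a declared separation: the chance of declaring it for an ineffective drug is not the one the protocol states.

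**Working it through.** **Inputs.** SD 14, 30 and 20 completers, 13-point effect (Protocol 9.1); threshold 0.90 (SAP 5.1); placebo prior N(13.7, 25), other priors vague (SAP Appendix 4). Drift means true placebo improvement minus 13.7. The documents give no range for it, so ±5 and ±10 (one and two prior SDs) are assumptions.

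**1. The protocol's power, without borrowing.** SE = 14 × √(1/30 + 1/20) = 4.041, and 13/4.041 = 3.217.
- One-sided 5%: Φ(3.217 − 1.645) = 94.2% (t-test 93.6%).
- Two-sided 5%: Φ(3.217 − 1.960) = 89.6% (t-test 88.3%).

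At these exact inputs only the one-sided reading is literally over 90%. This does not settle the matter: a modest reduction in residual SD from baseline adjustment brings the two-sided figure to 90% as well.

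**2. Operating characteristics of the SAP rule** (known SD 14, flat prior on the effect).
- Weight on placebo data: w = (20/196) / (20/196 + 1/25) = 0.718. The prior's weight is 0.282, worth 196/25 = 7.8 placebo patients.
- Posterior SD of the effect: √(196/30 + 1/(20/196 + 1/25)) = √(6.533 + 7.040) = 3.684.
- Sampling SD of the posterior mean: √(196/30 + 0.718² × 196/20) = √(6.533 + 5.058) = 3.405.
- Bias: 0.282 × drift. Placebo doing better than the prior expects makes the drug look better.
- P(success) = P(Z > (z × 3.684 − 0.282 × drift − effect) / 3.405).

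At effect 0, drift 0 and threshold 0.90: 1.2816 × 3.684 / 3.405 = 1.387, which gives **8.3%**. Without borrowing both SDs are 4.041, so the error is exactly **10%**. Averaged over drift ~ N(0, 25), the variance is 3.405² + 0.282² × 25 = 13.57 = 3.684², so it is again **10%**.

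| Threshold | Error at drift −10 / −5 / 0 / +5 / +10 (%) | Power at 13 points, same drifts (%) | No borrowing: error, power (%) |
|---|---|---|---|
| 0.90 | 1.3 / 3.6 / 8.3 / 16.5 / 28.8 | 94.6 / 97.8 / 99.2 / 99.8 / 99.9 | 10.0, 97.4 |
| 0.95 | 0.5 / 1.4 / 3.8 / 8.6 / 17.0 | 88.7 / 94.8 / 97.9 / 99.3 / 99.8 | 5.0, 94.2 |
| 0.975 | 0.2 / 0.6 / 1.7 / 4.4 / 9.8 | 80.8 / 90.0 / 95.5 / 98.3 / 99.4 | 2.5, 89.6 |

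**3. Where the 0.90 rule crosses 5%.** Solve 1.2816 × 3.684 − 0.282 × drift = 1.645 × 3.405: drift = −3.1. The error exceeds one-sided 5% at any higher drift. Under the SAP's own prior that has probability Φ(3.12/5) = 73%. Drift of +5 or more has probability 16%, and +10 or more 2.3%.

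**4. Checks.** Simulating the full Appendix 4 model (baseline covariate, unknown variance, 4,000 trials per cell) gave errors at 0.90 of 1.6 / 3.4 / 8.3 / 17.6 / 29.4% over the same drifts. A separate simulation with 8,000 null trials per scenario gave 8.1% on target and 10.5% with the noninformative placebo prior. If baseline adjustment lowers the residual SD to 12 or 10 (assumed), the on-target error is 8.6% or 8.9%, and at +10 it is 26.5% or 24.0%.

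**The case against.** The best counter-case is that the 5% was never meant for the Bayesian rule. Protocol 9.1 is a planning statement that names no posterior threshold, Protocol 9.2.1 lists ANCOVA before the Bayesian analysis, the SAP's example ANCOVA code uses alpha 0.05, and SAP Appendix 1 lists ANCOVA under the primary endpoint. Protocol section 9 also lets the SAP modify the plan. On this view a one-sided level near 10% is an ordinary Phase 2a choice, and the sensitivity analyses would expose a result driven by borrowing.

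Part of this stands. A 10% one-sided level can be acceptable in Phase 2a, and the link between the 5% and the rule is inferred from shared wording. The power claim does not reveal the sidedness: two-sided t-test power reaches 90.0% at residual SD 13.6 and 92.4% at SD 13, and is 93.4% at SD 14 with 36 and 24 analysed (all assumed values).

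The rest does not remove the point. ANCOVA is a sensitivity analysis under SAP 6.1.2, so if the 5% belongs to it, the primary decision has no stated error rate. Sensitivity analyses help interpret a result but leave the primary rule's error unchanged, and the noninformative-prior model read at 0.90 itself runs at 10%. Protocol section 9 says major changes to the primary analysis will be reflected in a protocol amendment, and the SAP flags no change of error rate.

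**Conclusion.** The concern holds. The stated 5% is not a property of the primary decision rule on either reading. With the prior on target the one-sided error is 8.3%, about 1.7 times a one-sided 5% (8.3/5) and 3.3 times the 2.5% per side of a two-sided 5% (8.3/2.5). The 8–10% describes the on-target, prior-averaged and no-borrowing cases and is not an upper bound: the error reaches 16.5% at drift +5 and 28.8% at +10, and falls below 5% only when the true placebo improvement is more than about 3 points under 13.7.

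These figures rest on the protocol's SD of 14 and 30:20 completers and on assumed drift values. The on-target excess needs no drift, and it persists at residual SDs of 10 to 12. This should be fixed. It is a mismatch between the two documents and an undocumented operating characteristic, not evidence that the rule is unusable in an early-phase trial.

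**What to change.** State in Protocol 9.1 whether the 5% is one- or two-sided. Then do one of the following:

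- **(a)** Raise the SAP 5.1 threshold to 0.95 if one-sided, or 0.975 if two-sided. These give 5% and 2.5% per side without borrowing or averaged over the prior. On target they are stricter (3.8% and 1.7%); a threshold of 0.936 would give 5% on target.
- **(b)** Keep 0.90 and correct the protocol's 5% to about 10% one-sided.

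Either way, add a table to the SAP giving Type I error and power at placebo drift of 0, ±1 and ±2 prior SDs. The table is needed even under (a), because 0.95 still gives 8.6% at +5 and 17.0% at +10.

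The text change is small, but stating the sidedness or correcting the 5% edits the protocol, so it means an amendment with ethics approval (Protocol 12.1). Option (b) costs no power. Under (a), the known-variance formula takes on-target power from 99.2% to 97.9% (0.95) or 95.5% (0.975). Simulation of the full model is less favourable: 98.9% falls to 97.4% or 93.9%, and at drift −10 it falls from 93.1% to 85.1% or 74.5%, below the stated 90%. Without borrowing, 0.975 gives about 88–90%.
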